7.4 Response Assessments

Patients will be re-evaluated for response to treatment after 2 cycles of treatment. Response will be assessed at 8-week intervals (± 1 week) during study treatment. Patients with progressive disease (PD) or unacceptable toxicity should be discontinued from the study; patients with stable disease (SD) or response to therapy will continue treatment through 6 cycles.

The following assessments will be performed as clinically indicated:

- Bone marrow aspirate and biopsy (to confirm CR only) including:
 - Quantify percent myeloma cell involvement
 - Obtain bone marrow aspirate for cytogenetics [i.e., diploidy, del 13] and include number of metaphases analyzed

CONFIDENTIAL

STUDY DRUG: MLN9708
 FINAL PROTOCOL: 11 APRIL 2014
 AMENDMENT NUMBER 3: 11 FEBRUARY 2016

SCRI INNOVATIONS STUDY NUMBER: MM 42

VERSION 4

- Mutations detected in FISH studies [i.e., t(4:14); t(11:14); del 17p]
- If available, provide MRD by flow cytometry
- SFLC
- SPEP and serum protein immunofixation to determine M-protein
- UPEP, urine protein immunofixation (requires a 24-hour urine collection), and total protein in urine
- Serum quantitative immunoglobulins
- Known plasmacytomas, utilize same modality used to assess original disease (i.e., PET, MRI, CT, etc)

Above response assessment will be performed every 3 months for 2 years after completion of maintenance therapy until disease progression.

7.5 End-of-Treatment Visit

Patients are permitted to continue maintenance treatment with MLN9708 through 6 cycles. Patients may be discontinued before the end of 6 cycles due to disease progression, unacceptable toxicity, or the decision to discontinue treatment by the patient or the study physician. After withdrawal from or completion of protocol treatment, patients must be followed for any new AEs for 30 calendar days after the last dose of study drug.

Thirty days (± 3 days) days after completion of the planned study treatment period or early discontinuation, the following tests and observations will be conducted:

- Update of medical history
- Physical examination including a neurological evaluation, measurement of weight, and vital signs
- ECOG performance status
- Acute GVHD assessment with overall score
- Chronic GVHD assessment with overall score
- AE assessment
- Concomitant medication review of all medications taken for conditions other than GVHD
- Concomitant medication review specifically for GVHD prophylaxis since receiving the allogeneic transplant
- CBC, including 3-part differential (total neutrophil count including bands, lymphocytes, monocytes) hemoglobin, hematocrit, and platelets
- CMP to include: glucose, BUN, creatinine (creatinine clearance calculated by Cockcroft-Gault), sodium, potassium, chloride, calcium, phosphorus, magnesium, CO₂, ALT, AST, ALP, LDH, uric acid, total bilirubin, total protein, and albumin

CONFIDENTIAL

STUDY DRUG: MLN9708
 FINAL PROTOCOL: 11 APRIL 2014
 AMENDMENT NUMBER 3: 11 FEBRUARY 2016

SCRI INNOVATIONS STUDY NUMBER: MM 42

VERSION 4

- Urinalysis (dipstick; if abnormal microscopic performed as clinically indicated)
- Disease assessment:
 - Bone marrow aspirate and biopsy (to confirm CR only) including:
 - Quantify percent myeloma cell involvement
 - Obtain bone marrow aspirate for cytogenetics [i.e., diploidy, del 13] and include number of metaphases analyzed
 - Mutations detected in FISH studies [i.e., t(4:14); t(11:14); del 17p] to confirm CR
 - If available, provide MRD by flow cytometry
 - SFLC
 - SPEP and serum protein immunofixation to determine M-protein
 - UPEP, urine protein immunofixation (requires a 24-hour urine collection), and total protein in urine
 - Serum quantitative immunoglobulins
 - Known plasmacytomas, utilize same modality used to assess original disease (i.e., PET, MRI, CT, etc)

7.6 Follow-up

Please see Appendix D.

8. DRUG FORMULATION, AVAILABILITY, ADMINISTRATION, AND TOXICITY INFORMATION

8.1 MLN9708

Investigational Product	Dosage Form and Strength	Manufacturer
MLN9708	2.3, 3.0, and 4.0mg	Millennium Pharmaceuticals, Inc

8.1.1 Labeling, Packaging, and Supply

MLN9708 is an anticancer drug and as with other potentially toxic compounds caution should be exercised when handling MLN9708 capsules.

MLN9708 will be supplied for oral administration by Millennium Pharmaceuticals, Inc. Capsules will be supplied color-coded by strength and will be individually packaged in blisters with a paper backing for child resistance.

CONFIDENTIAL

STUDY DRUG: MLN9708
 FINAL PROTOCOL: 11 APRIL 2014
 AMENDMENT NUMBER 3: 11 FEBRUARY 2016

SCRI INNOVATIONS STUDY NUMBER: MM 42

VERSION 4

The study drug will be labeled and handled as open-label material, and packaging labels will fulfill all requirements specified by governing regulations. The immediate packaging will contain a statement to conform with US Food and Drug Administration (FDA) Investigational New Drug (IND) requirements as follows: Caution: New Drug - Limited by Federal (or United States) law to investigational use.

All study drugs must be kept in a secure place under appropriate storage conditions. MLN9708 capsules should be stored unopened at 2 to 8°C (36 to 46°F). The capsules are individually packaged in cold form foil-foil blisters in a child-resistant package. The 2.3-, 3.0-, and 4.0 mg capsules are supplied as a 1 x 3 blister card in a child-resistant cardboard wallet.

The SCRI Innovations must be granted access on reasonable request to check drug storage, dispensing procedures, and accountability records.

8.1.2 Storage and Handling

Upon receipt at the investigative site, MLN9708 should remain in the blister and carton provided until use or until drug is dispensed. The container should be stored at the investigative site refrigerated (36°F to 46°F, 2°C to 8°C). Ensure that the drug is used before the retest expiry date provided by Millennium. Expiry extensions will be communicated accordingly with updated documentation to support the extended shelf life.

Because MLN9708 is an investigational agent, it should be handled with due care. Patients should be instructed not to chew, break, or open capsules. In case of contact with broken capsules, raising dust should be avoided during the clean-up operation. The product may be harmful by inhalation, ingestion, or skin absorption. Gloves and protective clothing should be worn during cleanup and return of broken capsules and powder to minimize skin contact.

The area should be ventilated and the site washed with soap and water after material pick-up is complete. The material should be disposed of as hazardous medical waste in compliance with federal, state, and local regulations.

In case of contact with the powder (e.g., from a broken capsule), skin should be washed immediately with soap and copious amounts of water for at least 15 minutes. In case of contact with the eyes, copious amounts of water should be used to flush the eyes for at least 15 minutes. Medical personnel should be notified. Patients are to be instructed on proper storage, accountability, and administration of MLN9708, including that MLN9708 is to be taken as intact capsules.

8.1.3 Study Compliance

Study drug will be administered or dispensed only to eligible patients under the supervision of the investigator or identified sub-investigator(s). The appropriate study personnel will maintain records of study drug receipt and dispensing.

8.1.4 Preparation and Administration of MLN9708

Patients will receive their study medication at the study site. The batch number of the study drug dispensed to the patient should be entered on the eCRF, if applicable.

CONFIDENTIAL

STUDY DRUG: MLN9708
FINAL PROTOCOL: 11 APRIL 2014
AMENDMENT NUMBER 3: 11 FEBRUARY 2016

SCRI INNOVATIONS STUDY NUMBER: MM 42

VERSION 4

MLN9708 will be given on an empty stomach, with no food and fluids except for water and prescribed medications for 2 hours before and 1 hour after each dose. Each dose of MLN9708 will be given with approximately 8 oz (240 mL) of water. If the patient vomits after taking a dose, another dose should not be given that day, but dosing should resume at the time of the next scheduled dose.

8.1.5 Precautions and Risks Associated with Handling MLN9708

MLN9708 drug product is a cytotoxic anticancer drug. As with other potentially toxic compounds, caution should be exercised when handling MLN9708. Please refer to published guidelines regarding the proper handling and disposal of cytotoxic agents.

MLN9708 capsules must be administered as intact capsules and are not intended to be opened or manipulated in any way.

8.1.6 Potential Risks and Benefits

Please refer to the current MLN9708 Investigator's Brochure (IB) and its Safety Management Attachment (SMA) provided by Millennium.

MLN9708 is a modified dipeptide boronic acid proteasome inhibitor similar to b, which has a known safety profile [VELCADE PI]. The most frequent AEs reported to date in the ongoing MLN9708 phase 1 studies were anticipated based on preclinical data and previous experience with VELCADE, and are noted in the IB, the Safety Management Attachment, and the informed consent documents. However, it is possible that MLN9708 will have toxicities that were not previously observed in or predicted from such sources. Patients will be monitored closely for anticipated toxicities.

MLN9708 shows early signs of antitumor activity as evidenced by at least a 50% reduction in disease burden in some patients and prolonged disease stabilization in others across all ongoing trials (Chow et al. 2012, Assouline et al. 2012, Lonial et al. 2012, Kumar et al. 2012 (a), Kumar et al. 2012 (b), Richardson et al. 2012 (c), San Miguel et al. 2012).

8.2 Accountability for All Study Drugs

The Principal Investigator (or designee) is responsible for accountability of all used and unused study drug supplies at the site.

All study drug inventories must be made available for inspection by the Sponsor or its representatives and regulatory agency inspectors upon request.

At the end of the study, all SCRI Innovations Drug Accountability Record Form(s) will be completed by the site and sent to the SCRI Innovations Regulatory Department. Study drug supplies must not be destroyed unless prior approval has been granted by the Sponsor or its representative. Please contact SCRI Innovations regarding disposal of any study drug.

8.3 MLN9708 Destruction

Investigational MLN9708 (expired or end of study) should be destroyed on site according to the institution's standard operating procedure. Be sure to document removal and destruction on drug accountability logs.

CONFIDENTIAL

STUDY DRUG: MLN9708
FINAL PROTOCOL: 11 APRIL 2014
AMENDMENT NUMBER 3: 11 FEBRUARY 2016

SCRI INNOVATIONS STUDY NUMBER: MM 42

VERSION 4

9. RESPONSE EVALUATIONS AND MEASUREMENTS

Response and progression will be evaluated in this study using the International Myeloma Working Group Uniform Response Criteria (see Appendix E).

CR	Complete Response
sCR	subcategory: stringent complete response
VGPR	Very good partial response
PR	Partial response
SD	Stable disease
PD	Progressive disease

All response categories (CR, sCR, VGPR, PR, PD) require two consecutive assessments made at any time before the institution of any new therapy, as well as no known evidence of progressive or new bone lesions if radiographic studies were performed. Radiographic studies are not required to satisfy these response requirements. Bone marrow assessments are not required to be confirmed by repeat testing.

Complete response should be confirmed with a bone marrow biopsy for morphology and a bone marrow aspiration for flow cytometry, FISH, and cytogenetics performed locally. Additional confirmatory studies include SPEP, UPEP, immunofixation of blood and urine, and SFLC (see Appendix D).

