10.4.2 Efficacy Analysis

- PFS, defined as the time from the first day of study drug administration (Day 1) to disease progression as defined by the International Myeloma Working Group Uniform Response Criteria (see Appendix E), or death on study. Patients who are alive and free from disease progression will be censored at the date of last tumor assessment.
- OS, defined as the time from the first day of study drug administration (Day 1) or death on study. Patients who are alive will be censored at the date of last known date alive.

Progression-free survival and OS (efficacy secondary endpoints) estimates will be generated using Kaplan-Meier methods, both for all patients enrolled and those patients receiving the MTD. Two-year PFS and OS estimates with 95% confidence intervals (CIs), and median PFS and OS with 95% CIs, will be generated and reported accordingly.

The effect of MLN9708 on immune effector cells after allogeneic stem cell transplant will be analyzed by examining the difference in the actual change from baseline at Cycle 1 Day 4, Cycle 1 Day 8, Cycle 1 Day 15, and Cycle 2 Day 1, and the percentage change from baseline at Cycle 1 Day 4, Cycle 1 Day 8, Cycle 1 Day 15, and Cycle 2 Day 1, among those patients participating in the biomarker research component. Each analysis will be performed within dose level and total patients.

The following parameters will be examined:

- CD3+, CD4+, CD8+, CD45+, CD19+ and CD56+/CD16+ cell counts, by fluorescence-activated cell sorting
- Regulatory T cell counts by intracellular staining of FoxP3, and surface staining of CD4+ and CD25+ cells
- Inflammatory cytokine concentrations of IL-1 β , IL-6, IL-8, IL-10 and TNF- α .

CONFIDENTIAL

STUDY DRUG: MLN9708

SCRI INNOVATIONS STUDY NUMBER: MM 42

FINAL PROTOCOL: 11 APRIL 2014

AMENDMENT NUMBER 3: 11 FEBRUARY 2016

VERSION 4

For each parameter, the actual change from baseline and the percentage change from baseline, at each time point, will be analyzed using the two-sided Wilcoxon signed-rank procedure to test whether either the change is statistically different from zero.

The significance level will be set at 10%, and there will be no adjustment to the alpha level for multiple comparisons. The rationale for the reporting of p-values in these analyses is for hypothesis-generating purposes only.

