- ^m Bone marrow aspirate and biopsy – quantify percent myeloma cell involvement, and obtain bone marrow aspirate for cytogenetics [i.e., diploidy, del(13)] and FISH studies [i.e., t(4:14); t(11:14);del(17p)], and at the response assessments to confirm CR only. If available, provide MRD by flow cytometry at baseline.
- ⁿ Skeletal survey (lateral radiograph of the skull, anteroposterior and lateral views of the spine, and anteroposterior views of the pelvis, ribs, femora, and humeri) ≤ 28 days of first study drug treatment. Only repeat if clinically indicated (i.e., bone pain).
- ^o UPEP requires the collection of a 24-hour urine sample.
- ^p Repeat if abnormal at baseline.
- ^q All patients will undergo the end of treatment visit assessments listed within 30 days after treatment ends due to completion of the planned study treatment period, or once a patient is discontinued due to unacceptable toxicity or decision to discontinue treatment by the patient or the study physician. If treatment is discontinued because of toxicity or any other reason(s) at a treatment visit and no study treatment is administered, that visit may fulfill the End of Treatment Visit. After withdrawal from or completion of protocol treatment, patients must be followed for AEs for 30 calendar days after the last dose of study drug.
- ^r Patients who discontinue study treatment prior to the occurrence of disease progression will be followed every 3 months during years 1 and 2.
- ^s After disease progression is documented, patients will be followed every 3 months during years 1 and 2 for survival assessment.
- ^t For known plasmacytomas, utilize the same modality used to assess original disease (i.e., PET, MRI, CT, etc).
-

CONFIDENTIAL

STUDY DRUG: MLN9708

SCRI INNOVATIONS STUDY NUMBER: MM 42

FINAL PROTOCOL: 11 APRIL 2014

AMENDMENT NUMBER 3: 11 FEBRUARY 2016

VERSION 4

Page 79 of 86

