1.2 Study Design	
Study Type	 Non-Randomized  Randomized (Allocation Ratio:)
Details	
This is a Phase II, open-label, multicenter, non-randomized study to determine the feasibility of MLN9708 as maintenance after allogeneic stem cell transplant for multiple myeloma. Patients will be enrolled between Days 45 and 120 after allogeneic transplant and will receive MLN9708 on Days 1, 8, and 15 of each 28-day cycle for 6 cycles. Up to 18 patients will be enrolled in the dose-escalation phase to define the MTD of MLN9708. An additional 20 patients will be enrolled in the expansion phase at the MTD.
 
PFS is defined as the time from the first day of study drug administration (Day 1) to disease progression as defined by the International Myeloma Working Group Uniform Response Criteria (see Appendix E of protocol), or death on study. Patients who are alive and free from disease progression will be censored at the date of last tumor assessment.
 
OS is defined as the time from the first day of study drug administration (Day 1) to death on study. Patients who are alive will be censored at the date of last known date alive.
 
PFS and OS (efficacy secondary endpoints) estimates will be generated using Kaplan-Meier methods, both for all patients enrolled and those patients receiving the MTD. Two-year PFS and OS estimates with 95% confidence intervals (CIs), and median PFS and OS with 95% CIs, will be generated and reported accordingly.

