Efficacy Assessment Timepoints:	Patients will be re-evaluated for response to treatment after 2 cycles of treatment. Response will be assessed at 8-week intervals (±1 week) during study treatment. Patients with progressive disease (PD) or unacceptable toxicity should be discontinued from the study; patients with stable disease (SD) or response to therapy will continue treatment through 6 cycles.

Efficacy Endpoints:	
  
 	Endpoint	Primary Analysis Population	Other Analysis Population	
   
 Primary	PFS	Efficacy Evaluable		
 
 Secondary	OS	Efficacy Evaluable		
  
		Endpoint	Primary Analysis Population	Other Analysis Population	Primary	PFS	Efficacy Evaluable		Secondary	OS	Efficacy Evaluable							
	Endpoint	Primary Analysis Population	Other Analysis Population																
Primary	PFS	Efficacy Evaluable																	
Secondary	OS	Efficacy Evaluable																	
Definition of Terms:																			
 Response	 Complete Response + Partial Response as best observed response  Complete Response + Partial Response, confirmed with _____ weeks apart.  Other criteria, specify: International Myeloma Working Group Uniform Response Criteria: sCR (stringent complete response) CR (complete response) VGPR (very good partial response) PR (partial response) SD (stable disease) PD (progressive disease)																		
 Clinical Benefit	 Complete Response + Partial Response + Stable Disease as best observed response  Complete Response + Partial Response (confirmed with _____ weeks apart) + Stable Disease (at least _____ weeks from start of treatment)  Other criteria, specify:																		
 Progression	As reported by Investigator																		
 Subsequent Therapy																			
 Treatment Failure																			

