Definition of Endpoints:	Start Date:  Date of Randomization  Date of First Treatment End Date (specify for all pertinent endpoints): Progression-Free Survival: Event = Progression or Death 
  
 Situation	Date of Event or Censoring	Outcome	
   
 No baseline assessment	Date of first treatment	Censored	
 
 PD documented between scheduled visits, did not die, and received no subsequent therapy	First date of evaluated overall response = PD	Event	
 
 PD documented between scheduled visits, did not die, but received subsequent therapy prior to incurring progression event	Date of last evaluable tumor assessment prior to start of subsequent therapy	Censored	
 
 Death while on-study without previous PD, and received no subsequent therapy	Date of death	Event	
 
 Death while on-study and had previous PD, and received no subsequent therapy	First date of evaluated overall response = PD	Event	
  
	Situation	Date of Event or Censoring	Outcome	No baseline assessment	Date of first treatment	Censored	PD documented between scheduled visits, did not die, and received no subsequent therapy	First date of evaluated overall response = PD	Event	PD documented between scheduled visits, did not die, but received subsequent therapy prior to incurring progression event	Date of last evaluable tumor assessment prior to start of subsequent therapy	Censored	Death while on-study without previous PD, and received no subsequent therapy	Date of death	Event	Death while on-study and had previous PD, and received no subsequent therapy	First date of evaluated overall response = PD	Event
Situation	Date of Event or Censoring	Outcome																	
No baseline assessment	Date of first treatment	Censored																	
PD documented between scheduled visits, did not die, and received no subsequent therapy	First date of evaluated overall response = PD	Event																	
PD documented between scheduled visits, did not die, but received subsequent therapy prior to incurring progression event	Date of last evaluable tumor assessment prior to start of subsequent therapy	Censored																	

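### The protocol asks for two consecutive assessments before PD is accepted, the SAP counts the first reported PD, and neither says whether one PD assessment followed by new therapy is a PFS event

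*Protocol*

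**What the plan says.** **Confirmation rule.** Protocol Section 9 names PD explicitly: "All response categories (CR, sCR, VGPR, PR, PD) require two consecutive assessments made at any time before the institution of any new therapy". Footnote a of Appendix E applies the same rule to all categories. Section 9 gives one exemption: "Bone marrow assessments are not required to be confirmed by repeat testing".

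**PFS definition.** Protocol 10.4.2 defines the event as "disease progression as defined by the International Myeloma Working Group Uniform Response Criteria (see Appendix E), or death on study". SAP 1.2 uses the same definition: "disease progression as defined by the International Myeloma Working Group Uniform Response Criteria (see Appendix E of protocol), or death on study".

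**SAP operating rules.** Under 5/6 Efficacy, the SAP takes progression "As reported by Investigator". Its PFS table dates a progression event at "First date of evaluated overall response = PD". Other rows censor a patient who starts subsequent therapy before the progression event, at the last evaluable tumor assessment before that therapy. None of these rows mentions confirmation.

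**Schedule.** Protocol 7.4 says of follow-up: "Above response assessment will be performed every 3 months for 2 years after completion of maintenance therapy until disease progression". Appendix D then says: "After disease progression is documented, patients will be followed every 3 months during years 1 and 2 for survival assessment".

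**The concern.** Two-year PFS is a secondary objective in both documents, and the SAP efficacy table lists it as the primary efficacy endpoint. Its value depends on what counts as progression. A patient who shows PD once and then starts another treatment is a common and important case in myeloma follow-up, and the documents support opposite codings of that patient.

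If the patient is censored, the censoring is not neutral. It removes patients who have just met the PD thresholds and were judged to need treatment, so the remaining risk set looks better than it is. The error can only raise PFS. The study is open-label, so if the rule is left unstated, whoever programs the analysis chooses it when the data are already visible.

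**Working it through.** The plan states no PFS assumption, event count or power, so there is no plan figure to reproduce. The check compares the texts and then sizes the gap under stated assumptions.

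**1. One patient, three readings.** Take a patient in follow-up with one assessment meeting PD on M-protein, no repeat test, then new therapy.

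| Rules applied | Coding |
|---|---|
| SAP table, first reported PD is the event | Event at that assessment |
| Section 9 confirmation plus SAP therapy rows | No progression event yet; censored before the new therapy, and a later death does not restore the event |
| Section 9 confirmation plus protocol 10.4.2 alone | No censoring at new therapy; event only at death on study, otherwise censored at last tumor assessment |

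The SAP table does not settle the choice. Both rows that date an event at the first PD are limited to patients who received no subsequent therapy. The therapy rows cover therapy that came before the progression event. PD followed by therapy has no row of its own.

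**2. Is a second assessment scheduled?** On treatment, PD leads to discontinuation. Section 7.5 places an end-of-treatment visit with disease assessment 30 ± 3 days later, but an Appendix D note lets the discontinuation visit serve as that visit. In follow-up, assessments are 3 months apart, and after documented progression only survival is scheduled.

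**3. How much of the window is follow-up?** Treatment lasts 6 × 28 = 168 days, and the end-of-treatment visit falls near Day 198.
- After Day 168: (730.5 − 168)/730.5 = 77%.
- After Day 198: f = (730.5 − 198)/730.5 = 0.729.
- Under a constant hazard, with true 2-year PFS of 30/50/70%, the share of 2-year progressions arising after Day 198 is 60/66/69%. For 50%: F(198) = 1 − 0.5^(198/730.5) = 0.171, and (0.5 − 0.171)/0.5 = 66%.

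**4. Size if follow-up PDs are censored.** Assume a constant hazard, all events PD, and a share u of PDs after Day 198 unconfirmed and censored. The full hazard then applies up to Day 198 and (1 − u) of it afterwards, so the estimate is S^(1 − u·f). The exponent is 0.818 for u = 25% and 0.636 for u = 50%.

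| True 2-year PFS | u = 25% | u = 50% |
|---|---|---|
| 30% | 37% | 47% |
| 50% | 57% | 64% |
| 70% | 75% | 80% |

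A simulation on the scheduled visits (weeks 8, 16 and 24, Day 198, then every 3 months), censoring at the visit before the unconfirmed PD, gives 38/57/75% for u = 25% and 46/64/80% for u = 50%.

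If only 80% of events were PD (an assumption), the exponent is 1 − 0.8·u·f. A true 50% then becomes 0.5^0.854 = 55% for u = 25% and 0.5^0.708 = 61% for u = 50%.

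**5. Dating alone.** In the same simulation with every PD confirmed, dating at the first PD visit gives 31/51/71%. Dating at the next scheduled visit gives 36/55/74%.

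**The case against.** The strongest reply is that the texts can be read together, and much of it stands. It rules out four stronger readings that a reader might infer.

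- **That the two documents define different PFS events.** Both cite Appendix E, so the footnote reaches both. The first-PD entry can be read as the date given to a PD that was later confirmed, and investigator reporting says who assesses, not by which criterion. This is an unreconciled ambiguity, partly inside the SAP, not a flat contradiction.
- **That disease assessments stop at the first PD.** Section 7.4 says only until progression, and Appendix D says once it is documented. Under Section 9 that can mean confirmed progression.
- **That follow-up progressions cannot be confirmed.** Section 9 sets no minimum interval, so an unscheduled repeat before new therapy would do, and marrow findings need no repeat. The supported statement is that confirmation is required but not scheduled.
- **That the bias reaches 66%.** That figure, 0.5^(1 − 0.8 × 0.5), applies the unconfirmed share to all PD, including on-treatment PD, where an end-of-treatment disease assessment exists.

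Two further points are fair. The bias arises only if strict confirmation is applied; if every first PD counts, it does not occur. PFS is also imprecise: at 50% with 38 patients, a simple binomial 95% half-width is 1.96·√(0.25/38) = 16 points, which covers the 57% to 64% range. That limits what can be concluded from the estimate, but a wide interval does not excuse a one-directional bias that wording can remove.

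What the reply does not answer is the case in step 1. No sentence in either document says how to code it.

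**Conclusion.** The point holds as an unreconciled event definition. Section 9 and Appendix E require two assessments for PD, the SAP table uses the first with no confirmation condition, and follow-up schedules no confirmatory assessment once progression is documented. Whether one PD followed by new therapy is a PFS event is undecided, and so is the date of a confirmed PD.

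Read with the confirmation rule, the SAP censors such patients informatively and biases 2-year PFS upward. For a true 50%, the estimate would be about 57% to 64% if 25% to 50% of follow-up PDs were unconfirmed and censored. That range rests on a constant hazard, on all events being PD, and on unconfirmed shares that appear nowhere in the documents. With at most 38 patients, one reclassified patient is 1/38 = 2.6 points; in 26 patients at the MTD (6 + 20) it is 3.8 points.

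PFS is descriptive and untested, and the MTD and safety results do not change. The correction should be made, but the study's primary objectives do not depend on it.

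A related drafting fault supports the need to rewrite. Section 9 and footnote a also require, for every category, no known progressive or new bone lesions. That cannot apply to PD, because new lytic lesions are themselves a PD criterion in Appendix E. PD may have been included in that sentence by mistake.

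**What to change.** For the PFS analysis only, state the following in Section 9, Section 10.4.2 and the SAP event table:

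1. The event is dated at the first assessment that meets Appendix E PD.
2. A PD with no repeat test before death, new therapy or the end of assessment counts as an event.
3. PD is set aside only if a repeat test before new therapy contradicts it.
4. PFS with strictly confirmed PD is reported as a sensitivity analysis.

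Add a row to the SAP table for PD followed by subsequent therapy. Remove PD from the bone-lesion condition in Section 9 and footnote a.

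The cost is wording and one extra table. No visits or patients are added, and clinical management is unchanged. The downside is that a few single-value fluctuations may count as events. Appendix E limits this for M-protein: it requires a rise of at least 25% from nadir, plus an absolute rise of at least 0.5 g/dL to at least 1 g/dL in serum, or an absolute rise of at least 200 mg/24h in urine.
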